4.3.1.1 Premedication Regimen in Subjects Without a Prior Infusion Reaction

Consult the Sponsor for further guidance regarding premedication management eg, alternative medications for subjects allergic or intolerant to any premedication or to determine if locally used equivalent medications are acceptable.

On weeks of elotuzumab infusion, the weekly dexamethasone will be split into a po and IV administration (described in Section 4.3.1) which will also serve as premedication for elotuzumab.

Intravenous and po dexamethasone doses are calculated to prevent an imbalance in dexamethasone exposure between the control and investigational arms (Refer to Section 4.3.1.2 for premedication in subjects with prior infusion reaction).

In addition, the following must also be administered 30 - 90 minutes prior to elotuzumab:

- H1 blocker: diphenhydramine (25 - 50 mg po or IV) or equivalent;
- H2 blocker: ranitidine (50 mg IV) or equivalent
- acetaminophen (650 - 1000 mg po)

4.3.1.2 Premedication Regimen in Subjects With a Prior Infusion Reaction

To be re-treated with elotuzumab, subjects with prior infusion reaction must receive H1, H2 blockers and acetaminophen at maximum doses specified (ie, 50 mg diphenhydramine, 50 mg ranitidine, and 1000 mg acetaminophen).

To prevent imbalance in dexamethasone exposure between the two arms in the study, doses of intravenous dexamethasone above 10 mg require a decrease in the po dexamethasone. Recommended dexamethasone dosing is summarized below and in Table 4.3.1.2-1. Decisions to use more aggressive premedication schemes in subjects with only prior Grade 1 or only one prior Grade 2 infusion reaction must be approved by the Sponsor or designee.

- For subjects with prior Grade 1 infusion reaction, the same dexamethasone premedication regime as in Section 4.3.1 may be used.
- For subjects with prior Grade 2 infusion reaction, administer 10 mg IV dexamethasone (instead of 8 mg) as the premedication steroid at least 45 minutes prior to elotuzumab. Subjects should still take 28 mg oral dexamethasone either as a single dose or split dose (16 mg 12 - 24 hours AND 12 mg at least 3 hours prior to elotuzumab).
- For subjects with Grade 3 or recurrent Grade 2 elotuzumab infusion reactions, consultation with the Sponsor or designee is recommended. For these subjects, administer 18 mg IV dexamethasone as the premedication steroid at least 45 minutes prior to elotuzumab. To prevent imbalance in dexamethasone exposure between the two arms in the study, on the weeks that subjects receive 18 mg IV dexamethasone, they must only receive a total of 16 mg oral dexamethasone (8 mg 12 - 24 hours AND 8 mg at least 3 hours prior to elotuzumab). Eighteen mg of IV dexamethasone has similar exposure to approximately 24 mg oral dexamethasone.

Table 4.3.1.2-1: Corticosteroid Premedication^a	
Prior Infusion Reaction	Corticosteroid Premedication^b Prior to Elotuzumab
None or Only Grade 1 infusion reaction ^c	28 mg po dexamethasone (3 - 24 hrs prior to elotuzumab) AND 8 mg IV dexamethasone at least 45 min prior to elotuzumab
Prior Grade 2 infusion reaction ^d	28 mg po dexamethasone (3 - 24 hrs prior to elotuzumab) AND 10 mg IV dexamethasone at least 45 min prior to elotuzumab
Prior Grade 3 or recurrent Grade 2 infusion reaction	8 mg oral dexamethasone (12 - 24 hrs prior to elotuzumab) AND 8 mg oral dexamethasone (at least 3 hrs prior to elotuzumab) AND 18 mg IV dexamethasone at least 45 min prior to elotuzumab

^a For prior infusion reactions, use maximum doses H1, H2 blockers and acetaminophen as described in [Section 4.3.1.2](#).

^b At the discretion of the investigator, the oral dexamethasone component may be given as a split dose 12 - 24 and 3 hours prior to elotuzumab.

^c Subjects with prior Grade 1 infusion reaction may be premedicated as per Grade 2 infusion reactions.

^d Subjects with prior Grade 2 infusion reaction may be premedicated as per Grade 3 infusion reactions.

If a subject with a prior Grade 2 - 3 infusion reaction also requires dose reduction of dexamethasone, the weekly dexamethasone on the days of elotuzumab infusion should be no lower than 8 mg IV (on the day of elotuzumab infusion at least 45 minutes prior to elotuzumab).

The oral portion of dexamethasone may be split between the day prior and day of infusion as this may further reduce the incidence of infusion reactions. For example, for subjects with only a prior Grade 1 infusion reaction, the following split dose may be given: 12 mg dexamethasone po (12 - 24 hrs prior to elotuzumab) **AND** 16 mg dexamethasone po (at least 3 hrs prior to elotuzumab) **AND** 8 mg IV dexamethasone at least 60 minutes prior to elotuzumab.

Subjects with Grade 4 infusion reaction are not eligible to receive additional elotuzumab. These subjects should still continue to receive lenalidomide and dexamethasone.

4.3.2 Guidelines for Elotuzumab Infusion in Subjects with Infusion Reactions

4.3.2.1 Grade 1 Infusion Reaction

Grade 1 elotuzumab infusion-related reactions by definition, require no intervention; however, increased monitoring is recommended.

4.3.2.2 Grade ≥ 2 Infusion Reaction

Infusion reactions during the elotuzumab infusion: For a Grade ≥ 2 elotuzumab infusion-related reaction, the infusion must be interrupted. The subject should be treated as clinically indicated with one or more of the following medications or interventions: antiemetics, antihistamines, analgesics, corticosteroids, leukotriene inhibitors, oxygen inhalation, epinephrine, bronchodilators, or other supportive measures as indicated. Subjects with a Grade 4

elotuzumab infusion reaction must have elotuzumab permanently discontinued. These subjects should continue to receive lenalidomide and dexamethasone per protocol.

Once the elotuzumab infusion-related reaction has resolved to Grade ≤ 1 , the infusion can be restarted at 0.5 mL/minute. If symptoms do not recur after 30 minutes, the infusion rate may be increased in a stepwise fashion **starting at a rate per investigator's discretion, and increasing up to a rate per investigator's discretion, up to a maximum of 5 mL/minute.**

Subjects who experience an infusion reaction require vital signs to be monitored every 30 minutes for 2 hours after the end of the elotuzumab infusion. If the elotuzumab infusion reaction recurs, the infusion must be stopped and not restarted on that day. Appropriate therapy should be administered to address the subject's signs and symptoms. The infusion can be reattempted at the next protocol defined infusion time point at the investigator's discretion with additional premedication as described in [Table 4.3.1.2-1](#)

Infusion reactions after the completion of elotuzumab infusion: Should a Grade ≥ 2 infusion reaction occur following completion of an elotuzumab infusion, the subject should be treated as clinically indicated with 1 or more of the following medications or interventions: diphenhydramine, acetaminophen, hydrocortisone, H2 inhibitor, leukotriene inhibitor, oxygen inhalation, epinephrine, bronchodilators, or other supportive measures as indicated.

Elotuzumab infusions on subsequent weeks after a prior Grade ≥ 2 infusion reaction: Subjects with prior Grade 2 or higher infusion reactions should have the next infusion started at 0.5 ml/min and then escalated in a stepwise fashion (0.5 mL/minute every 30 minutes to a maximum of 2 mL/min). If no Grade ≥ 2 infusion reaction occurs, the next infusion may be **increased in a stepwise fashion starting at a rate per investigator's discretion, and up to a maximum of 5 mL/minute. If tolerated, all subsequent infusions may start at a rate per investigator's discretion, up to a maximum rate of 5 ml/minute.**

4.3.3 Dose Delay or Interruption

If the dose of one drug in the regimen (ie, lenalidomide, dexamethasone or elotuzumab) is delayed or interrupted, the treatment with the other drugs may continue as scheduled. Subjects experiencing a 28 day delay in all study drugs lenalidomide, dexamethasone, and elotuzumab due to an adverse event(s) related to study treatment must be discontinued from study drug. Subjects experiencing delays unrelated to study therapy, for example due to radiation therapy may delay study treatment up to 42 days. Delays greater than 28 days must be discussed with the medical monitor.

Each cycle is 28 days. While dose delays or interruptions are permitted, the start of each cycle cannot be delayed and is fixed relative to Cycle 1 Day 1. Adjustments to the Cycle 1 Day 1 anchored schedule should not be performed. Missed doses should be skipped, not delayed, if not given within the allowed window.

Subjects may continue on study therapy even if components of the study therapy must be discontinued. For example, a subject on lenalidomide and dexamethasone may continue on study therapy even if dexamethasone must be discontinued for an adverse event. Likewise, a subject on

the investigational arm may continue on study therapy if elotuzumab must be discontinued for an adverse event or other reason. Patients are considered still on study therapy even if they continue solely on lenalidomide.

Please consult the BMS medical monitor or any questions regarding dose interruption or study therapy discontinuation.

4.3.3.1 Elotuzumab

In Cycle 1 and 2, an elotuzumab dose that falls outside of the pre-specified window (-1 to +3 days) must be skipped.

In Cycles 3 and beyond, elotuzumab dosing may be delayed for up to 1 week. If unable to administer within 1 week, then the dose should be skipped and resumption of the elotuzumab continues per the protocol defined schedule.

4.3.3.2 Dexamethasone

Dexamethasone delay should be performed as clinically indicated at the discretion of the investigator.

For subjects receiving elotuzumab, the weekly dexamethasone dose that coincides with or is temporally closest to the elotuzumab dosing must be administered as part of the premedication for elotuzumab per the guidance in [Section 4.3.1](#).

4.3.3.3 Lenalidomide

Lenalidomide delay should be performed as clinically indicated at the discretion of the investigator.

Subjects should be instructed that if a dose of lenalidomide has been missed and it has been less than 12 hours since the subject's regular dosing time, to take lenalidomide as soon as the subject remembers. If it has been more than 12 hours, the dose must be skipped. Subjects should not take 2 doses at the same time.

4.3.4 Recommended Dose Reductions

The criteria presented in this section for dose modification are meant as general guidelines, and they are based on current US standards of clinical practice. Local standards may differ and may be followed. Dose modification may occur in the setting of lower grade toxicity if the investigator, in consultation with the Medical Monitor/Sponsor, believes that it is in the interest of subject safety.

4.3.4.1 Elotuzumab

No dose reduction is allowed for elotuzumab.

4.3.4.2 Dexamethasone Reductions

Dexamethasone dose reductions for toxicity must be performed as clinically indicated. Recommended management is described in [Table 4.3.4.2-1](#) and [Table 4.3.4.2-2](#). Deviations to the recommended dose reductions are allowed based on the clinical judgment of the investigator.

Table 4.3.4.2-1: Dexamethasone Dose Reductions		
CTCAE CATEGORY	ADVERSE EVENT	TREATMENT ADJUSTMENT
Gastrointestinal	Dyspepsia, gastric or duodenal ulcer, gastritis Grade 1 - 2 (requiring medical management)	Treat with a proton pump inhibitor. If symptoms persist despite above measures, decrease by one dose level.
	≥ Grade 3 (requiring hospitalization or surgery)	Hold dexamethasone until symptoms adequately controlled. Reduce by one dose level and resume along with concurrent therapy with a proton pump inhibitor. If symptoms persist despite above measures, reduce to dose level -3.
	Acute pancreatitis	Reduce to dose level -3.
Cardiovascular	Edema ≥ Grade 3 (limiting function and unresponsive to therapy or anasarca)	Use diuretics as needed, and decrease dexamethasone by one dose level. If edema persists despite above measures, decrease by another dose level.
Neurology	Confusion or Mood alteration ≥ Grade 2 (interfering with function ± interfering with activities of daily living)	Hold dexamethasone until symptoms resolve. Decrease by one dose level and resume. If symptoms persist despite above measures, decrease by another dose level.
Musculoskeletal	Muscle weakness ≥ Grade 2 (symptomatic and interfering with function ± interfering with activities of daily living)	Hold dose until muscle weakness is ≤ Grade 1. Decrease dexamethasone by 1 dose level and resume. If weakness persists despite above measures, decrease by another dose level.
Metabolic	Hyperglycemia ≥ Grade 3 or higher	Treat with insulin or oral hypoglycemics as needed. If uncontrolled despite above measures, decrease by one dose level until levels are satisfactory.
Constitutional	Insomnia ≥ Grade 2	Decrease by one dose level and resume.

Dose reduction for persistent Grade 2 or Grade ≥ 3 AEs believed to be related to dexamethasone and not listed above are permitted. Dose reductions should follow guidance in Table 4.3.4.2-1 and [Table 4.3.4.2-2](#).

For subjects receiving elotuzumab, regardless of dexamethasone dose reduction, at least 8 mg of the weekly dexamethasone dose must be administered IV as part of the premedication for elotuzumab with the remainder of the weekly dexamethasone dose administered orally as described in [Section 4.3.1](#). Contact the medical monitor to discuss dexamethasone IV premedication for subjects in the investigational arm who reach dose level -3 and must discontinue oral dexamethasone due to dose limiting toxicity.

On weeks without elotuzumab, no IV dexamethasone should be administered.

Dose Level	Weeks with Elotuzumab		Weeks without Elotuzumab	
	PO	IV	PO	IV
0	28 mg	8 mg	40 mg	0 mg
-1	12 mg	8 mg	20 mg	0 mg
-2	0 mg	8 mg	12 mg	0 mg
-3	0 mg	contact Medical Monitor	0 mg	0 mg

4.3.4.3 Lenalidomide

Dose adjustments, as summarized below, are recommended for the management of NCI CTCAE Grade 3 and 4 toxicities for thrombocytopenia, neutropenia or other toxicities that are judged by the investigator to be related to lenalidomide. Information in Table 4.3.4.3-1 and Table 4.3.4.3-2 is based on current standard of clinical practice.

When Platelet Counts:	Recommended Course

 Fall to $< 30,000/\text{mm}^3$ Return to $\geq 30,000/\text{mm}^3$ 	Interrupt lenalidomide treatment; follow complete blood counts weekly. Resume lenalidomide at 15 mg, Days 1 - 21, once daily.
For each subsequent drop $< 30,000/\text{mm}^3$ Return to $\geq 30,000/\text{mm}^3$	Interrupt lenalidomide treatment. Resume lenalidomide at 5 mg less than previous dose, Days 1 - 21, once daily. Do not dose below 5 mg.

When Neutrophil Counts:	Recommended Course
Fall to $< 1000/\text{mm}^3$ Return to $\geq 1000/\text{mm}^3$ and neutropenia is the only toxicity	Interrupt lenalidomide treatment, add G-CSF; ^a follow complete blood counts weekly. Resume lenalidomide at 25 mg, Days 1 - 21, once daily.
Return to $\geq 1000/\text{mm}^3$ and if other toxicity	Resume lenalidomide at 15 mg, Days 1 - 21, once daily.
For each subsequent drop $< 1000/\text{mm}^3$ Return to $\geq 1000/\text{mm}^3$	Interrupt lenalidomide treatment. Resume lenalidomide at 5 mg less than previous dose, Days 1 - 21, once daily. Do not dose below 5 mg.

In case of neutropenia, consider the use of growth factors in subject management.

^a G-CSF = Granulocyte Colony-Stimulating Factor

Lenalidomide Dose Adjustments in Subjects with Renal Impairment

Since lenalidomide is primarily excreted via the kidney, adjustments to the dose of lenalidomide are provided based on the lenalidomide country prescribing information. The regimen of 21 day dosing every 28 days remains the same despite the dose reductions described below.

Table 4.3.4.3-3: Lenalidomide Dose Adjustments in Subjects with Renal Impairment^a	
Creatinine Clearance (CRCL):	Recommended Course
Moderate renal impairment (30 ≤ CRCL < 60 mL/min)	10 mg, every 24 hours
Severe renal impairment (CRCL < 30 mL/min, not requiring dialysis)	15 mg every 48 hours
End Stage Renal Disease (CRCL < 30 mL/min, requiring dialysis)	5 mg once daily. On dialysis days, dose should be administered following dialysis

^a Source: Lenalidomide USPI

Dose Adjustments During Treatment for Other Grade 3 and 4 Toxicities

Angioedema, Grade 4 rash, exfoliative or bullous rash, Stevens-Johnson syndrome or toxic epidermal necrolysis requires permanent discontinuation of lenalidomide. For Grade 2 - 3 skin rash judged to be related to lenalidomide interruption or discontinuation should be considered.

For other Grade 3 and 4 toxicities judged to be related to lenalidomide, hold treatment and restart lenalidomide at the next lower dose level when toxicity has resolved to ≤ Grade 2.

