A by-subject listing for dose omission will be presented for all treated subjects. This listing will include all reported omissions per CRF, regardless of whether the subject had a computed omission based on the actual dosing dates.

- **Dose Interruption**

The number and percentage of subjects with any interruption in their elotuzumab infusion, with 1, 2, 3, or \geq 4 interruptions, with an interruption due to “infusion reaction”, “infusion administration issues” and “other” will be presented. In addition, duration of interruptions (in minutes) will be summarized via descriptive statistics.

A by-subject listing will be generated for elotuzumab IV interruptions. This listing will include reason for interruption, whether the infusion was resumed, and duration of the interruption.

- **IV Rate Reduction**

The number and percentage of subjects with any elotuzumab IV rate reduction, with 1, 2, 3, or \geq 4 rate reductions, and with rate reductions due to “infusion reaction,” “infusion administration issues,” and “other” will be presented.

A by-subject listing will be generated for elotuzumab IV rate reductions.

Lenalidomide:

- **Dose Reduction**

Reduction of Lenalidomide will be computed based on the actual dose received. In any study day (excluding, cycle 1, day 1), the drug will have a calculated reduction compared to the previous day, if the actual level of the administered dose is below the actual level of the administered dose in the previous instance. The information for this analysis will be derived programmatically, using the total daily dose on the “Record of Study Medication - lenalidomide” eCRF page.

The daily dose levels are defined as follows:

- Dose level 0 or full dose (25 mg): \geq 20.0
- Dose level -1 (15 mg): 12.5 mg to < 20.0

- Dose level -2 or starting dose for moderate renal impairment (10 mg): 8.75 to < 12.5 mg
- Dose level -3 for subjects with severe renal impairment (15 mg every 48 hours): 6.25 to < 8.75 mg
- Dose level -4 for subjects with End Stage Renal Disease (ESRD) (5 mg): < 6.25 mg

The number and percentage of subjects with a dose reduction, and the lowest dose level achieved per subject (-1, -2, -3, \leq -4), will be presented by treatment group. This table will be broken out by whether the subject started at the standard dose level or at the 10 mg dose level.

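### The first lenalidomide re-start dose after a cytopenia is a fixed 15 or 25 mg with no cap, so it can contradict the 10 mg renal dose or reverse an earlier toxicity reduction

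*Protocol*

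**What the plan says.** Protocol 4.3.4.3 has three tables for lenalidomide.

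- **Platelets.** At the first fall below 30,000/mm³, treatment is interrupted. On recovery the advice is "Resume lenalidomide at 15 mg, Days 1 - 21, once daily".
- **Neutrophils.** At the first fall below 1000/mm³, treatment is interrupted and G-CSF added. If the count recovers "and neutropenia is the only toxicity", the advice is "Resume lenalidomide at 25 mg, Days 1 - 21, once daily". If there is other toxicity, it is 15 mg.
- **Renal impairment (Table 4.3.4.3-3).** For creatinine clearance of 30 to below 60 mL/min the dose is "10 mg, every 24 hours", on the same 21-of-28-day schedule. The text adds that "adjustments to the dose of lenalidomide are provided based on the lenalidomide country prescribing information".

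The neighbouring toxicity rules are relative to the current dose. For later falls in either count the rule is "Resume lenalidomide at 5 mg less than previous dose, Days 1 - 21, once daily", with a floor of 5 mg. For other severe toxicity attributed to lenalidomide, sites are to "hold treatment and restart lenalidomide at the next lower dose level". The protocol text does not number lenalidomide dose levels. SAP 7.4.1.2 lists the level below 25 mg as "Dose level -1 (15 mg").

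Subjects on 10 mg are expected. Protocol 3.3.2 (exclusion 3g) removes only clearance below 30 mL/min. SAP 7.4.1.2 treats 10 mg as the starting dose in moderate renal impairment and splits the dose-reduction table by starting dose. SAP 7.4.1.3 gives these subjects their own planned dose intensity.

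**The concern.** A fixed re-start dose is safe only if every subject was at or above that dose when treatment stopped. Two foreseeable groups were not:

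1. subjects whose dose had already been lowered for a different toxicity;
2. subjects on the 10 mg renal dose.

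For both, the written figure can point upward immediately after a neutrophil count below 1000/mm³ or a platelet count below 30,000/mm³. For the second group, two tables in the same section give different doses and no sentence ranks them. For the first group the renal table is no safeguard, because clearance may be normal.

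What is at stake is patient safety. The drug is given in both arms, so the ambiguity is common to both.

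**Working it through.** **Reproducing the plan's own figure.** Lenalidomide is taken on 21 of 28 days, so weekly dose = daily dose × 21/28 × 7 = daily dose × 5.25.

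- 25 mg: 25 × 5.25 = 131.25 mg/week, as in SAP 7.4.1.3.
- 10 mg: 10 × 5.25 = 52.5 mg/week, as in SAP 7.4.1.3.
- 15 mg: 15 × 5.25 = 78.75 mg/week.

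**Applying the first-fall rows as written.** Each ratio is the table dose divided by the dose before interruption. The last column shows the dose if the re-start were capped at the previous dose.

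| Dose before interruption | Table says 15 mg | Table says 25 mg | Capped dose (15 mg row / 25 mg row) |
|---|---|---|---|
| 25 mg | 15/25 = 0.60 | 25/25 = 1.00 | 15 / 25 mg |
| 15 mg (reduced for toxicity) | 15/15 = 1.00 | 25/15 = 1.67 | 15 / 15 mg |
| 10 mg (renal, or reduced for toxicity) | 15/10 = 1.50 | 25/10 = 2.50 | 10 / 10 mg |

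Only the 25 mg line behaves as a dose-reduction table should.

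**Earlier toxicity reduction, normal clearance.**

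1. The subject starts at 25 mg. A first platelet fall leads to 15 mg. This step uses the protocol alone. Another severe toxicity leads to the same dose if the SAP's levels are used.
2. The platelets (or other toxicity) recover. A first neutropenia follows, with nothing else present.
3. The neutrophil row gives 25 mg: 78.75 to 131.25 mg/week, a rise of 131.25 − 78.75 = 52.5 mg/week, or 1.67-fold.
4. Suppose instead that a second platelet fall had already taken the dose to 15 − 5 = 10 mg. A first neutropenia then gives 25 mg (2.5-fold), or 15 mg (1.5-fold) if the past thrombocytopenia is counted as other toxicity.

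A subject at 10 mg is therefore pointed upward under either reading of the neutrophil rows. A subject at 15 mg is pointed upward only when neutropenia is taken to be the sole toxicity.

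**Renal dose of 10 mg, clearance still 30 to below 60 mL/min.**

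- Renal table: 10/10 = 1.0-fold, 52.5 mg/week.
- Platelet row, or neutropenia with other toxicity: 15/10 = 1.5-fold, 78.75 mg/week.
- Isolated neutropenia: 25/10 = 2.5-fold, 131.25 mg/week.

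If the cytopenia tables were followed throughout, a second platelet fall would only return this subject to the starting dose (15 − 5 = 10 mg). After isolated neutropenia it would take three further falls (25 to 20 to 15 to 10 mg).

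The documents give no share of subjects with clearance of 30 to below 60 mL/min and no rate of sequential cytopenias. The number affected cannot be derived and is not estimated.

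**The case against.** The strongest reply is that no site is obliged to follow the rows. Protocol 4.3.4 concerns dose reductions, calls its criteria general guidelines and allows local standards. Protocol 4.3.3 directs questions about interruptions to the medical monitor, and Protocol 5.2 supplies the lenalidomide package insert to sites. A clinician would hardly read such a section as advice to raise a dose after a cytopenia. This stands as a limit on severity. It does not reconcile the tables: permission to use local practice does not say which of the protocol's own figures applies, and a site reading a single row may see no question to raise.

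Four narrower points:

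- **The renal table is a standing rule.** A fall in blood counts does not change clearance, so 10 mg arguably still applies. That is the sensible reading, but the text does not state it.
- **An earlier toxicity may count as other toxicity.** The re-start is then 15 mg and the 1.67-fold rise disappears. This is fair for a subject at 15 mg. It does not help a subject at 10 mg.
- **The SAP dose levels classify exposure and are not dosing instructions.** True, but the platelet route to 15 mg does not depend on them.
- **The text is incomplete.** The captions of the two cytopenia tables are not visible in the available text, and other parts of the protocol are redacted. A caption could limit scope to a 25 mg start. The conclusion therefore covers only the rows and text shown.

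**Conclusion.** The concern holds as a minor safety-wording fault. The first re-start rows are fixed at 15 or 25 mg, while the neighbouring toxicity rules are relative to the current dose, and nothing in the visible text of the section caps them.

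Followed as written, they raise the dose 1.67-fold for a subject previously cut to 15 mg who then has a first isolated neutropenia. They raise it 1.5- or 2.5-fold for a subject on 10 mg. For renal subjects they contradict Table 4.3.4.3-3 with no order of precedence. Subjects on 25 mg are dosed as intended.

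The 1.67-fold figure assumes that a resolved earlier toxicity does not count as other toxicity. The 1.5-fold figure for a 10 mg subject holds even if it does. For renal subjects, both increases assume that the cytopenia table is followed over the renal table. No endpoint, power or type I error is affected.

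**What to change.** Add one footnote to Tables 4.3.4.3-1 and 4.3.4.3-2:

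> The re-start dose must not exceed the dose before the interruption or the current renal-adjusted dose in Table 4.3.4.3-3. Where a reduction is called for and the subject was already at or below 15 mg, consult the medical monitor or local prescribing information for the next lower dose.

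The footnote limits only the dose at re-start after a cytopenia. It does not prevent a later increase if renal clearance recovers. A binding limit in an advisory table has a precedent here, since the same tables already set a 5 mg floor.

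The cost is one footnote on two tables, by amendment or administrative letter. No visit, procedure, data item or analysis changes.
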